## LIST OF ABBREVIATIONS

AE	Adverse Event/Adverse Experience
ASA	American Society of Anesthesiologists
ASES	American Shoulder and Elbow Surgeons Standardized Shoulder Assessment Form
C-ISB	Continuous Interscalene Nerve Block
CFR	Code of Federal Regulations
CRF	Case Report Form
DSMB	Data and Safety Monitoring Board
FDA	Food and Drug Administration
GCP	Good Clinical Practice
HIPAA	Health Insurance Portability and Accountability Act
IB	Investigator's Brochure
IRB	Institutional Review Board
LANSS	Leeds Assessment of Neuropathic Symptoms and Signs
LAST	Local Anesthetic Systemic Toxicity
LB-SISB	Liposomal Bupivacaine Single injection interscalene blockade
NRS	Numeric Rating Scale
OBAS	Overall Benefit of Analgesic Score
OME	Oral Morphine Equivalents
PACU	Post-anesthesia Care Unit
PHI	Protected Health Information
PI	Principal Investigator
POD	Postoperative Day
QoR-15	Quality of Recovery 15-item short form patient survey
RASS	Richmond Agitation-Sedation Scale
SAE	Serious Adverse Event/Serious Adverse Experience
TDABC	Time-Driven Activity-Based Costing
TSA	Total Shoulder Arthroplasty

Title	Prospective, randomized clinical trial comparing analgesic efficacy of liposomal bupivacaine single-injection interscalene blockade to continuous interscalene blockade for patients undergoing primary total shoulder arthroplasty
Running Title	LB-SISB vs CISB
Protocol Number	21-000908
Phase	Phase IV
Methodology	Single center, unblinded, randomized control trial with two intervention arms
Overall Study Duration	14 Months (time when data collected for last patient)
Subject Participation Duration	Up to 7 days post-operatively
Single or Multi-Site	Single-Site
Objectives	Primary objective is to assess analgesia efficacy between liposomal bupivacaine single injection interscalene blockade vs. continuous interscalene nerve block for patients undergoing primary total shoulder arthroplasty. Secondary objectives include pain scores and opioid consumption at pre-defined time intervals, peripheral nerve block complications, length of hospital stay, and postoperative follow-up for up to 7 days after surgery depending on follow-up availability.
Number of Subjects	88 patients will be randomized to one of two interventions: liposomal bupivacaine single injection interscalene blockade or continuous interscalene nerve block.

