### **3 Study Design**

#### **3.1 General Design**

Single center, unblinded, randomized control trial with two intervention arms assessing acute pain management. These two arms include: 1) liposomal bupivacaine single-shot interscalene blockade (LB-ISB group) and 2) continuous interscalene nerve block (C-ISB group)

The study will be registered with [www.ClinicalTrials.gov](http://www.ClinicalTrials.gov)

After approval by Mayo Clinic IRB, we will work closely with the department of orthopedics at Mayo Clinic Hospital, Methodist Campus to enroll patients into the study. Potential subjects will consist of patients who present for elective primary TSA meeting the inclusion and exclusion criteria (Section 4.1 and 4.2). Subjects will be approached by study staff for recruitment in person and informed consent will be obtained during the preoperative clinic visit. Prior to surgery, subjects will be randomized to either one of the two study groups using dynamic allocation in a computer application developed by personnel in the Division of Biomedical Statistics and Informatics (Section 7.3). Subjects unable to give consent themselves will not be approached for participation. No remuneration will be provided. All efforts will be made to enroll participants regardless of ethnic heritage. No passive recruitment methods (newspapers, advertisements, or flyers) will be used.

Eighty-eight patients are required for this clinical trial. After baseline values are established, data will prospectively be collected during the peri-operative period up to 7 days post-operatively (patient will have follow-up via office visit or telephone call) for the purpose of this study. Data will be collected utilizing the institution's electronic medical record system and be transferred to an electronic research database (e.g. Excel, REDCap). Figure 1 and Table 1 summarizes the data that will be collected during this study.

Study Activity	Pre-	Peri- & Post-operative	
	operative	Pre-op	POD 0 (day of surgery)
Informed Consent	X		
Inclusion/Exclusion Criteria	X		
Pain Scores (numeric rating scale)	X	X	X
Patient and Surgical Data Collections	X	X	
OBAS			X
QoR-15 Patient Survey	X		X
Opioid Consumption		X	X
Length of Hospital Stay			X
Adverse Events Monitoring		X	X
Peripheral Nerve Block - catheter related complications		X	X
Follow up via telephone call or office visit		X	X*

Table 1. Summary of data collection

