### 4.3 *Early Withdrawal of Subjects*

#### 4.3.1 **When and How to Withdraw Subjects**

If the patient is unable to comply with the study protocol or they wish to withdraw from the study their participation in the study will be terminated. Furthermore, if the placement of the peripheral nerve blocks cannot be performed, if an unanticipated reoperation is performed (during the same hospital stay), if an unanticipated complication unrelated to the study (e.g. pulmonary embolism, myocardial ischemia) where patients are unable to participate in study protocol, or if the patient remains intubated and sedated postoperatively for greater than one day, the patient will be terminated from the study. If the interscalene nerve block catheter becomes occluded or is pulled out prematurely, patients will remain in the study as our primary analysis will be performed based on the intention to treat.

In order to account for 10% dropout, which includes patients terminated from the study, a total sample-size of N = 88 (44 per group) is proposed. Follow-up will not be performed for patients terminated from the study.

If the patient chooses not to participate, he or she will be provided the current perioperative care plan in place by the surgeon which will include various pain management options regardless of participation.

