# 8 Statistical Plan

## 8.1 Sample Size Determination

Sample size calculations were performed based on the outcomes of pain (NRS) and opioid consumption (OME) measured at 24 hours after surgery. Using data from [name] et al, the standard deviations of NRS pain and opioid consumption were estimated to be 2.4 points and 23.6 mg OME for the single injection inter-scalene block group and 2.3 points and 25.1 mg OME for the continuous interscalene block group, respectively. Assuming that similar variability will be observed in the proposed study, a sample of 40 subjects in each arm (n=80 total) will provide 80% power to detect a difference of at least 1.5 points in NRS pain and 20 mg OME measured at 24 hours post-surgery. In order to protect against a potential drop-out rate of 10%, a total of 88 subjects will be enrolled. Calculations were based on a two-sample t-test, with alpha=0.05, two-sided test.

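### Figure 1 shows 74 patients (37 per arm) where the text sets the trial at 88, and 74 is below the 80 subjects on which Section 8.1 rests its 80% power

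*Combined protocol and SAP*

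**What the plan says.** Four places in the text agree on the total:

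- Synopsis, Number of Subjects: "88 patients will be randomized to one of two interventions".
- Section 3.1: "Eighty-eight patients are required for this clinical trial".
- Section 4.3.1: "a total sample-size of N = 88 (44 per group) is proposed". This is the only place that states a per-group figure of 44.
- Section 8.1: "In order to protect against a potential drop-out rate of 10%, a total of 88 subjects will be enrolled".

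Section 8.1 gives the basis: "a sample of 40 subjects in each arm (n=80 total) will provide 80% power". The target differences, both at 24 hours, are 1.5 points for NRS and 20 mg for OME.

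Figure 1, in Section 3.1, follows patients from recruitment to follow-up. It shows 74 patients in the recruitment and consent box, then 1:1 allocation on the day of surgery, then 37 patients in each of the LB-ISB and C-ISB boxes. Section 3.1 refers the reader to this figure, so it is current protocol content.

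**The concern.** A protocol should give one target sample size, and this one gives two. The figure is consistent with itself (37 + 37 = 74), so a single misread digit does not explain it. It also cannot be matched to any number in the text: it is neither the 88 to be recruited, nor the 80 in the power statement, nor what is left of 88 after the planned drop-out.

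What is at stake is when accrual ends. Someone working from the diagram could regard the trial as complete 14 patients before someone working from the text. The trial is unblinded (Section 7.8), so its planned end of accrual should not be open to two readings. The sample size is also the number on which the stated power depends, and the pain outcome has almost no slack at 40 per arm.

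**Working it through.** **Inputs, all from Section 8.1**

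- Test: "Calculations were based on a two-sample t-test, with alpha=0.05, two-sided test".
- Differences to detect: 1.5 NRS points and 20 mg OME.
- Standard deviations: "2.4 points and 23.6 mg OME for the single injection inter-scalene block group"; 2.3 points and 25.1 mg OME for the continuous block group.
- Drop-out: 10%.

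**Step 1. Common SD (root mean square of the two arms)**

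- NRS: √((2.4² + 2.3²)/2) = √((5.76 + 5.29)/2) = √5.525 = 2.351
- OME: √((23.6² + 25.1²)/2) = √593.5 = 24.36

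**Step 2. Reproduce the plan's own figure**

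Power comes from the noncentral t distribution with 2n − 2 degrees of freedom and noncentrality δ = difference / (SD × √(2/n)), where n is the number per arm.

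- NRS, n = 40: δ = 1.5 / (2.351 × √0.05) = 2.854, and power is 80.5%. The smallest n per arm that reaches 80% is 40.
- OME, n = 40: δ = 20 / (24.36 × √0.05) = 3.671, and power is 95.2%. OME alone needs only 25 per arm, so NRS sets the sample size.
- Inflation: 80 × 1.10 = 88, the stated total. Dividing instead, 80 / 0.90 = 88.9, gives 89, which is one patient more and immaterial here.

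The 40 per arm and the 88 both reproduce.

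**Step 3. Can 74 be derived from 88 or 80?**

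- 88 less 10%: 88 × 0.90 = 79.2, not 74.
- 88 − 74 = 14, and 80 − 74 = 6.
- In Figure 1 the 74 stands at consent, before randomization, so it cannot be a count after drop-out.

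**Step 4. Power if accrual followed Figure 1**

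| Per arm | How it arises | NRS power | OME power | NRS difference detectable with 80% power |
|---|---|---|---|---|
| 40 | Section 8.1 basis | 80.5% | 95.2% | 1.49 |
| 37 | 74, no loss | 77.3% | 93.6% | 1.55 |
| 33.3 | 74 × 0.90 / 2 | 72.7% | 91.0% | 1.64 |
| 33 | the same, whole patients | 72.3% | 90.7% | 1.65 |

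For n = 37: δ = 1.5 / (2.351 × √(2/37)) = 2.745 for NRS, and 20 / (24.36 × √(2/37)) = 3.531 for OME.

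**Step 5. Sensitivity to the SD**

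With one arm's SD used for both arms, NRS power at 37 per arm is 75.6% (SD 2.4) or 79.0% (SD 2.3). Both are below 80% under the t-test that 8.1 names. A normal approximation with SD 2.3 gives 80.1%, but 8.1 specifies the t-test and 40 per arm.

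For comparison, 44 per arm with no loss gives NRS power of 84.1%.

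**The case against.** The strongest reply is that the governing text leaves no real doubt. Four places say 88, the calculation in 8.1 leads to 88, and no analysis or stopping rule uses 74 or 37. Section 3.1 introduces Figure 1, together with Table 1, as a summary of data collection and not as the source of the sample size. The sentence giving 88 is in the same paragraph. On this view the figure is an uncorrected diagram, and the loss of power is hypothetical. Most of this stands. It is why the point is a consistency correction and not a fault in the design. It does not remove the contradiction, which concerns the size of the trial and is explained nowhere.

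Three stronger readings are tempting, and the documents do not support them:

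- *The trial is underpowered, or 8.1 is miscalculated.* Section 8.1 reproduces. A shortfall arises only if recruitment stops at Figure 1's number, and nothing in the document says that it will. The 72–73% figure needs a further assumption, that 74 is a number still to lose 10%.
- *Every one of the four places says 44 per arm.* Only Section 4.3.1 does. Elsewhere it follows from 88 and 1:1 allocation.
- *It is unclear whether 88 counts enrolled or randomized patients.* Section 8.1 does use the looser verb, and consent precedes randomization. But the synopsis counts patients randomized, and a per-group count in 4.3.1 exists only after allocation. Read together, these largely settle 88 as a randomized number. Figure 1 shows no loss between consent and allocation, so it does not bear on the question.

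**Conclusion.** The inconsistency is real and should be fixed. Figure 1 is the likely outlier, because the text agrees on 88 throughout and the arithmetic in 8.1 supports it. The document cannot say where 74 came from, so the sponsor has to confirm which number is operative.

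The size of the consequence is conditional and modest. If 74 were the number accrued, NRS power would be about 3 percentage points lower than at 40 per arm (77.3% against 80.5%) with no loss, and about 8 points lower if 10% of the 74 then dropped out. The detectable NRS difference would move from just under the 1.5 points named in Section 3.2 to just over it. OME power would stay above 90% in every case. These figures assume the differences and SDs in 8.1, equal arms, a root-mean-square SD and the two-sided t-test at 0.05.

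**What to change.** Correct Figure 1 to 88 patients, with 44 in each arm box. This changes three numbers in one diagram and does not affect the design, the analysis or the power statement.

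If the sponsor confirms that 74 is the operative target, make the opposite change. Replace 88 in the synopsis, 3.1, 4.3.1 and 8.1, and 44 in 4.3.1. Restate NRS power in 8.1 as about 77% with no loss and about 72–73% after 10% loss. The cost is a less favourable power statement.

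Optionally, change the verb in the last part of 8.1 so that it counts patients randomized, as the synopsis does. This is a wording alignment only.

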#### **4.3.2 Data Collection and Follow-up for Withdrawn Subjects**

Patients who voluntarily withdraw from the study, are terminated due to unforeseen circumstances such as reoperation, or if intubated and sedated postoperatively for greater than one day, will have their data collected in the peri-operative and follow-up periods up to the point of termination. Our primary analysis will be performed based on the intention to treat. A subgroup analysis will also be performed on patients who received the allocated treatment as per the planned protocol.

The safety profile for liposomal bupivacaine has been assessed in previous studies as mentioned in Section 1.3, and the primary outcome for this study involves assessing its analgesic efficacy compared to other standard methods of regional anesthesia acute pain management techniques for patients undergoing total shoulder arthroplasty. Survival data for liposomal bupivacaine will not be assessed in this study; thus, we will plan to exclude data after a patient's termination/withdrawal date.

If the patient chooses not to participate, he or she will be provided the current perioperative care plan in place by the surgeon and will include various pain management options regardless of participation.

## **5 Study Procedures**

### **5.1 Pre-op Plan**

All patients will undergo a standardized multimodal analgesia total joint pathway (See attached document). Preoperatively, patients will be sedated, under the discretion of the anesthesiologist, with intravenous midazolam (1-4 mg) and fentanyl (50-200 mcg) for alleviation of anxiety and pain. Additional sedatives at the discretion of the anesthesia team. The interscalene nerve block will be performed under continuous live ultrasound guidance, obtaining visualization of the roots (C5-C6 is ideal) or trunks (Superior Trunk is ideal) of the brachial plexus in between the anterior and middle scalene muscles as described by Chan. An in-plane or out-of-plane approach to needle advancement under live ultrasound guidance will be at the discretion of the anesthesiologist. In cases with poor ultrasound imaging, a combined nerve stimulator and ultrasound guidance technique is acceptable. Appropriate needle placement will be verified by injecting normal saline 0.9% and visualizing spread within the interscalene groove at the level of the roots/trunks of the brachial plexus. Local anesthetic may also be used for hydrodissection to navigate needle placement into the correct position. The proceduralist should attempt to use less than 10 mL of normal saline 0.9% to identify correct placement of peripheral nerve block.

For patients randomized to C-ISB group, a continuous catheter device (Perifix ® Catheter, B.Braun, Bethlehem, PA, USA) will be placed within the interscalene groove at the level of the roots/trunks of the brachial plexus. After delivery of the catheter, verification of the catheter within the interscalene groove will be assessed by again evaluating spread of normal saline 0.9% or local anesthetic within the interscalene groove.

## 5.2 Dosing

The local anesthetic solutions used for each block are displayed in Figure 2. The initial loading dose for the continuous ISB group will be administered through the nerve catheter. The ambulatory nerve catheter system (On-Q CB004, Avanos Medical, INC., Alpharetta, GA) will be connected to the nerve catheter and the infusion rate will be initiated at 8 mL/hr. Infusion rate changes will be at the discretion of the operating room anesthesiologist and, subsequently, the acute pain service. Patients discharged with the ambulatory nerve catheter system will be managed using our institutional protocol which includes patient/family instructions, daily follow-up, and a dedicated team to cover concerns or questions 24 hours, 7 days a week (<http://intranet.mayo.edu/charlie/anesthesiology-perioperative-medicine-rst/anesthesia-home/divisions/ce-anesthesia/continuous-nerve-catheters-pilot/#tabs-16274-0-0>).

Treatment Arm	Local Anesthetic	Total Volume of Preoperative Bolus	Infusion
Liposomal Bupivacaine Interscalene Nerve Block (LB - SISB)	5 mL of Bupivacaine 0.5% mixed with 10 mL of liposomal bupivacaine (133 mg)*	15 mL	N/A
Continuous Interscalene Nerve Block (CISB)	Bupivacaine 0.5% with 1:200,000 Epinephrine (premixed solution)	15-20 mL	On-Q Select-A-Flow CB004 pump with continuous infusion of bupivacaine 0.2% at 8 mL per hour for 72 hours

Figure 2. Treatment Arms.

*\* In accordance with manufacturer prescribing guidelines: max dose of liposomal bupivacaine of 133 mg and mixing ratio of standard bupivacaine HCl to liposomal bupivacaine of less than 1:2 (25 mg / 133 mg)*

### 5.3 Assessment

Patients in both groups will undergo sensory testing to evaluate block success. Sensory testing is as follows, sensation to cold over the deltoid muscle (0= absent or diminished, 1 = at baseline). Motor block will be assessed by deltoid contraction (0= absent or diminished, 1 = at baseline). Block will be assessed at least 25 minutes after the placement of the block, if pre-surgical time permits, or postoperatively in the recovery room, or patients' room on POD 0. This assessment will be charted in the electronic anesthesia medical record when it has been completed.

### 5.4 Intra-op Plan

Intraoperative anesthetic management entails general endotracheal anesthesia with standard American Society of Anesthesiologists monitoring. All patients will receive 8 mg of intravenous (IV) dexamethasone. Intraoperative opioids, antiemetic prophylaxis, and additional intraoperative monitoring (e.g., arterial line) are at the discretion of the attending anesthesiologist.

### 5.5 Postoperative Management

Postoperatively, all study patients will follow a standardized multimodal analgesia total joint pathway (see attached document). Medical care will be co-managed by both the orthopedic surgery team and anesthesia acute pain service, which is comprised of a regional anesthesiologist, anesthesia resident, and trained nursing staff. This service provides 24-hour in-hospital coverage with daily patient rounding to act on potential concerns associated with continuous local anesthetic infusion.

multimodal  
protocol TSA 12272

TSA Study Post-op  
(standardized meds,1

## 6 Safety Endpoints

These methods are already established procedures in the practice of perioperative pain control for a total shoulder arthroplasty. There is minimal risk of placing a peripheral nerve block. Those risks include infection, bleeding, and/or nerve damage. Patients will be monitored during the perioperative period for any adverse events. During regional anesthesia block placement,

trained sedation nurses or anesthesia personnel (staff physicians, residents, or nurse anesthetists) will be monitoring patients. Patients will be monitored throughout the procedure utilizing the American Society of Anesthesiologists (ASA) standard monitors\*, aspirating for blood or cerebral spinal fluid prior to administration of local anesthetic solution in divided doses, frequent assessment of the patient's well-being via verbal communication, and always having emergency medications and airway equipment readily available. Performing this regional block (ISB) is considered standard in our practice to provide optimal postoperative analgesia.

*\* blood pressure (non-invasive blood pressure cuff cycling every 3 to 5 minutes or continuous arterial blood pressure monitoring placed due to clinical judgment of covering anesthesiologist), 5 lead EKG, continuous pulse-oximetry, and continuous monitoring from operating room anesthesia personnel (if the procedure is performed in the operating room) or frequent assessments by nurses who are trained to care for patients receiving regional anesthesia blocks (if procedure is performed in block room)*

Patients that are not discharged the same day after surgery will be admitted to the regular nursing floors. Vital signs (heart rate, oxygen saturation, and blood pressure) will be captured every 4 to 6 hours or more frequently if the clinical situation dictates in all postoperative orthopedic patients.

Patients admitted to the hospital will be followed daily by the acute pain service and surgical team. Patients discharged with a continuous interscalene nerve block will be followed by the acute pain service team. All study patients, regardless of treatment arm and hospital status (inpatient vs outpatient), will be followed by study personnel. Adverse events and/or complications will be monitored, which includes but not limited to, local anesthetic systemic toxicity, neurologic complications, hematoma, bleeding, infection, and wound problems. Nerve damage and assessment is part of the follow-up regarding this study and will be followed closely. In the event an infection was to occur, the PI would be notified, protocol would be followed, and investigators of the study would review the incident.

The principal investigator or a designated co-investigator of the study will be notified if a patient in the study requires an unanticipated ICU admission.

## **7 Study Drug**

### **7.1 Description**

Liposomal bupivacaine (Exparel®) is supplied in one vial, containing either 133 mg or 266 mg (1.3%; 13.3 mg/mL) of bupivacaine suspended in multivesicular liposomes in normal saline. It is regularly stocked in our pharmacy and automated dispensing medication system (Pyxis Medstation) found in the operating rooms and procedure rooms due to its frequent use for postoperative pain control.

## **7.2 Treatment Regimen**

Patients randomized to LB-ISB will receive a preoperative single-injection interscalene block for pain management following primary total shoulder arthroplasty. The solution administered will contain 5 mL of bupivacaine 0.5% (25 mg) along with 10 mL of liposomal bupivacaine (133 mg), which conforms to manufacture recommended guidelines.

